9.6.1 Endpoint Analyses

The following non-safety endpoints will be analyzed using the AEECS considering the actual study arm (i.e. product use exposure). The following sections describe the statistical models used in analyzing the endpoints as well as descriptive statistics used for summarizing the data.

In general, for model based analysis all visit data will be used and analyzed within the same model.

- 9.6.1.1 Statistical Analysis of Endpoints
- 9.6.1.1.1 To evaluate changes in VO₂max in subjects switching to IQOS (with and without training), continuing to smoke cigarettes (with training) and being smoking abstinent

A linear mixed effects model will be used to estimate the difference in VO₂max between each arm (SA arm, IQOS-1+IQOS-2 combined arm, Dual-1+Dual-2 arm) versus cigarette arm one week after randomization (V4) and after completion (SA arm, IQOS-1 arm, IQOS-2 arm, Dual-1 arm) of the 12-week training program (V43). The degrees of freedom will be adjusted by using Kenward Roger (KR) method and the Saitterthwaite method will be used in case of convergence issues. Both V4 and V43 data will be used together in the same model. At V4, both IQOS-1 and IQOS-2 will be combined into a single IQOS group as these subjects did not attend any exercise training.

The dependent variable will be the VO₂max change from baseline with baseline VO₂max, arm, visit, sex, age and visit*arm as *fixed* covariates and subject fitted as a random effect. In addition, the following *exploratory* covariates BMI, RPC, COHb levels at each visit, cigarette consumption at V1, IPAQ score at V1, average step count 2 weeks prior to visit, self-reported daily cigarette consumption (from randomization until each visit), cigarette smoking 30-60 minutes before test for subjects in cigarette arm and IQOS use 30-60 minutes before test for subjects in IQOS arm will be assessed for adequacy in the model using a step-wise (backward) approach through the following algorithm.

Data and information contained in this document are considered to constitute trade secrets and confidential commercial information, and the legal protections provided to such trade secrets and confidential information are hereby claimed under the provisions of applicable law. No part of this document may be publicly disclosed without the written consent of Philip Morris Products S.A

Philip Morris Products SA.	Statistical Analysis Plan	Confidential
P1-EXC-01-EU	Final 2.0	Page 40 of 71
Related to PMI-RRP-WKI-112487		

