## 2.2 Purpose of the Study

This study is part of the global clinical assessment program of *IQOS* which is designed to provide scientific evidence to further substantiate the potential of reduced risk of using *IQOS* as compared to smoking cigarettes. The main goals of this exploratory study are to assess whether switching from cigarette smoking to using *IQOS* will influence 1) VO2max and exercise capacity, 2) ability to perform exercise training and thereby influence 3) VO2max after 12 weeks of exercise training, 4) physiological parameters and biological health markers, and finally 5) physical activity levels in daily life.

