8.3 As Exposed Exercise Compliant Set

The As Exposed Exercise Compliant Set (AEECS) consists of all randomized subjects who have at least one valid non-safety assessment after randomization, specifically we have

- post-randomization product (cigarette or IQOS) use experience if randomized to IQOS, • IQOS-2 or cigarette arm or
- no product use if randomized to the SA arm,

and who attended at least 34 of 38 (~90%) of the exercise training sessions except the subjects in IQOS-2 arm. Subjects in the IQOS-2 will be analyzed as exposed as they did not participate in the training. The AEECS will be analyzed by actual exposure (product use exposure, actual study arm).

Due to technical issues with the bike training equipment during the study, these rules are used to determine if a subject completed a training session for the purposes of defining the AEECS analysis set in addition to information regarding whether a training visit was done or not. We define a training session to be completed if a minimum of 20 or more minutes of exercise was done. If the training time is unknown then the session is considered to be not done. These checks from the protocol deviation dataset will be done regardless of whether data from the exercise training is available or not.

For a training session to be considered as not done from the protocol deviations (PD) dataset, the PD description will be checked for the following,

- "Bike training was not done" •
- "Bike training was partially completed for less than 20 min ..."
- "Bike training was partially completed for unknown number of minutes ..."

A bike training session is considered as complete if the following description for bike training is provided in the PD dataset,

- "Bike training was completed..."
- "Bike training was partially completed for at least 20 min..." •

In the case where there are inconsistencies between the PD dataset and bike training data, ie, for example bike training was marked as complete but the PD descriptions says otherwise, the PD rules will be used to determine completion of a bike training session.

Confidentiality Statement

Philip Morris Products SA.	Statistical Analysis Plan	Confidential
P1-EXC-01-EU	Final 2.0	Page 32 of 71
Related to PMI-RRP-WKI-112487		

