9.6.1.3 Supportive/Sensitivity Analyses

If deemed appropriate, selected endpoint analyses will additionally be performed for the FAS.

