Table 15.2.2.2.14: Variable Selection in Analysis of Change in Time to Complete	
Table 15.2.2.14: Variable Selection in Analysis of Change in Time to Complete the Exercise Capacity Test from Baseline – AEBECS	
Table 15.2.2.15: Descriptive Statistics for Time to Complete the Exercise	
Capacity Test: Acute and Training Effect Variables – AEBECS	
Table 15.2.2.2.16: Sensitivity Analysis of Change in Time to Complete the	
Exercise Capacity Test from Baseline (Acute Effect, V4) – AEECS	
Table 15.2.2.17: Sensitivity Analysis of Change in Time to Complete theExercise Capacity Test from Baseline (Training Effect, V43) – AEECS	
Table 15.2.2.18: Regression Coefficients for Sensitivity Analysis of Change in	
Time to Complete the Exercise Capacity Test from Baseline – AEECS	
Table 15.2.2.19: Variable Selection in Sensitivity Analysis of Change in Time	
to Complete the Exercise Capacity Test from Baseline – AEECS	
Table 15.2.2.2.0: Sensitivity Analysis of Descriptive Statistics for Time to	
Complete the Exercise Capacity Test: Acute and Training Effect Variables –	
AEECS	
Table 15.2.2.3.1: Analysis of the Intensity of the Exercise Training (Change	X
from Baseline in Cumulative Work Produced) at V14, V28 and V42– AEECS	
Table 15.2.2.3.2: Regression Coefficients for Analysis of the Intensity of	
Exercise Training (Change from Baseline in Cumulative Work Produced) –	
AEECS	
Table 15.2.2.3.3: Descriptive Statistics for Intensity of Exercise Training - AEECS	X
Table 15.2.2.3.4: Descriptive Statistics for Intensity of Exercise Training by	x
Intervals at V5, V14, V29 and V41 - AEECS	
Table 15.2.2.4.1.1: Analysis of the Changes in Blood Composition Parameters	x
from Baseline (Training Effect, V43) – AEECS	
Table 15.2.2.4.1.2: Regression Coefficients for Changes in Blood Composition	x
Parameters from Baseline – AEECS	
Table 15.2.2.4.1.3: Descriptive Statistics of Blood Composition Parameters –	x
AEECS	
Table 15.2.2.4.2.1: Analysis of the Changes in Respiratory Parameters from	
Baseline (Acute Effect, V4) – AEECS	
Table 15.2.2.4.2.2: Analysis of the Changes in Respiratory Parameters from	
Baseline (Training Effect, V43) – AEECS	
Table 15.2.2.4.2.3: Regression Coefficients for Changes in Respiratory	
Parameters from Baseline – AEECS	
Table 15.2.2.4.2.4: Descriptive Statistics of Respiratory Parameters – AEECS	
Table 15.2.2.4.3.1: Analysis of the Change in Workload from Baseline at a	X
Lactate Level of 4mmol (Exercise Effect, V43) – AEECS	^

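### Training intensity (objective 3) is planned only in subjects who completed at least 34 of 38 sessions and only by product used; an analysis by randomised arm and an attendance table should be added

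*SAP*

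**What the plan says.** Protocol section 2.2 lists the main goals of the study. The second begins "ability to perform exercise training and thereby influence" and leads on to VO2max after the 12-week programme. Objective 3 is the only objective that measures the training itself. It is worded as training intensity, with work, work rate, heart rate and time in intensity zones per session as endpoints.

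SAP section 9.6.1 sets the population and grouping for all these endpoints: "The following non-safety endpoints will be analyzed using the AEECS considering the actual study arm (i.e. product use exposure". Section 8.3 limits the AEECS to subjects with post-randomisation data "and who attended at least 34 of 38 (~90%) of the exercise training sessions except the subjects in IQOS-2 arm". It adds: "We define a training session to be completed if a minimum of 20 or more minutes of exercise was done". On grouping it says: "The AEECS will be analyzed by actual exposure (product use exposure, actual study arm".

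Sections 9.6.1.1.3 and 9.6.1.2.3 name no other set for objective 3. Every objective 3 table (15.2.2.3.1 to 15.2.2.3.4) and figure (15.1.3.1 to 15.1.3.4) carries the AEECS label, for example "Table 15.2.2.3.3: Descriptive Statistics for Intensity of Exercise Training - AEECS".

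The only opening to another set is section 9.6.1.3: "If deemed appropriate, selected endpoint analyses will additionally be performed for the FAS". It names no endpoint. The table list has FAS endpoint analyses for VO2max and exercise capacity, and none for objective 3.

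**The concern.** Whether a subject completes 34 sessions is known only after randomisation, and it may depend on how well that subject copes with training. If the arms differ in who passes, the subjects left in each group are no longer comparable, and a difference in training intensity mixes the effect of the product with the effect of selection. Regrouping by product actually used moves the comparison further from the randomised one, and subjects whose diaries place them in the Others group stay out of the statistical models.

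Information is also lost. The objective 3 model estimates V14, V28 and V42, yet a subject who trained normally through the first two of these and then stopped contributes nothing. No table reports sessions attended or completed by randomised arm, so the most direct evidence on ability to train would not be summarised at all.

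**Working it through.** **Threshold.** 34/38 = 0.895, which agrees with the plan's figure of about 90%. At most 38 − 34 = 4 sessions may be missed, be shorter than 20 minutes or have unknown duration.

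**What exclusion discards.** Session 1 is V5, so session k falls at visit k + 4. Session 34 is V38, and anyone who stops before V38 is excluded by construction. V14 is session 10 and V28 is session 24. A subject who completed every session up to V28 has data at two of the three modelled visits, and none of it is used. The most that one excluded subject can lose is 33 of 38 sessions (87%).

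**Planned dropout.** SAP section 6 allows about 20%: 0.20 × 25 = 5 per trained arm, or 15 of 75. Dropouts before V38 fail the rule before any exclusion for irregular attendance.

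**How the rule turns attendance into selection.** Assume independent sessions with completion probability p (my assumption; the documents give no attendance figure). The share passing is P(X ≥ 34) with X ~ Binomial(38, p):

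| p | share passing |
|---|---|
| 0.95 | 0.96 |
| 0.90 | 0.67 |
| 0.85 | 0.31 |
| 0.80 | 0.10 |

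A difference of five points in attendance (95% against 90%) becomes a difference of 29 points in who is analysed (96% against 67%).

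**Illustrative bias.** Assume that within each arm attendance and the training measure are jointly normal with correlation ρ, and that the top fraction p on attendance passes. The mean shift among those who pass is ρ·m(p), in SD of the training measure, where m(p) = φ(z)/p and z is the cut-off with P(Z > z) = p. This gives m(0.5) = 0.798, m(0.6) = 0.644, m(0.7) = 0.497 and m(0.8) = 0.350. The bias in the contrast (better-training minus worse-training arm) is ρ·[m(p better) − m(p worse)]:

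| pass rate, better arm | pass rate, worse arm | ρ = 0.3 | ρ = 0.5 | ρ = 0.7 |
|---|---|---|---|---|
| equal | equal | 0 | 0 | 0 |
| 70% | 60% | −0.044 | −0.074 | −0.103 |
| 70% | 50% | −0.090 | −0.151 | −0.211 |
| 80% | 60% | −0.088 | −0.147 | −0.206 |
| 50% | 70% | +0.090 | +0.151 | +0.211 |

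Negative values understate the contrast and positive values overstate it. The last row has the size of the second with the sign reversed.

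**Yardstick.** The plan sizes the study on VO2max only: 20 per arm, SD 14, half-width about 10.3 mL/kg/min with probability 90%. This reproduces: t(0.975, 38) × 14 × √(2/20) × √(χ²(0.90, 38)/38) = 10.23. Without the last factor the half-width is 8.96, and 8.96/14 = 0.64 SD. The bias in the table is smaller than the random error of one contrast. Unlike that error, it is not reflected in the confidence interval and does not shrink with more subjects.

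**The case against.** The protocol names the AEECS as the main set for non-safety analyses, and the study is declared descriptive with no hypothesis test. An as-exposed, exercise-compliant estimate is a legitimate exploratory target and fits the carbon monoxide rationale in protocol section 4.2. That stands, and it is why the AEECS analysis should be kept.

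Some information on excluded subjects is planned: reasons for exclusion and set sizes by arm (Tables 15.2.1.3 and 15.2.1.4), disposition at V14 and V28, a deviation summary (Table 15.2.1.6.1) and a bike-training listing for the Safety Set (15.3.6.2). These help a reader to see who left. They give neither a training estimate that includes those subjects nor session counts by randomised arm.

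Four stronger readings are tempting, and the documents do not support them.

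- A reader might infer that the analysis conditions on its own outcome. Attendance is not an objective 3 endpoint; the modelled outcomes are changes from V5 in work and work rate. What can be said is that the set is selected on a variable that may be related to them.
- A reader might infer that those removed are the subjects who could not train. Half of a 40-minute session counts, so many who struggle stay in. Missed visits for any reason, withdrawal and unknown training times also lead to exclusion.
- A reader might infer that the bias always runs toward no difference. That requires the worse-training arm to attend less. Protocol section 4.2 also foresees pressure to relapse in the abstinence arm during the intense programme; if that arm lost more subjects while training better, the sign would reverse.
- A reader might infer that VO2max and exercise capacity share the gap. Their FAS tables are already listed (15.2.2.1.6 to .10 and 15.2.2.2.6 to .10), and whether they carry a topline flag changes no result.

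**Conclusion.** The concern holds in a limited form. Objective 3 is committed only to a set selected on post-randomisation attendance and grouped by product used. Usable earlier sessions are discarded, and nothing planned shows training or attendance by randomised arm.

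The size cannot be known in advance. The only planning figure is one dropout rate of about 20% for all trained arms; equal pass rates would give no bias in this model. With a 10-point gap (70% against 60%) the bias is about 0.04 to 0.10 SD, and with a 20-point gap about 0.09 to 0.21 SD, in either direction. These values rest on the assumed pass rates, the normal model and correlations of 0.3 to 0.7, none of which is in the documents. The correlation of attendance with change from V5 may differ from that range. Expressing the bias as a share of a treatment effect would need an assumed true effect as well, and the plan gives none for objective 3.

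**What to change.** Keep the AEECS analysis. In SAP sections 9.6.1.1.3 and 9.6.1.3, commit without condition to a parallel version of Tables 15.2.2.3.1 to 15.2.2.3.4 on all trained-arm FAS subjects, by randomised arm, using every session with data. Add one table of sessions attended, sessions completed (20 minutes or more) and total training minutes by randomised arm.

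The data are already collected and the programs exist, so the cost is SAP wording and a few extra tables. The FAS estimates may look less clean than those in compliant subjects. They will also not remove every problem: a subject who stops contributes only up to the last session, and the mixed model then relies on the remaining data being missing at random. The attendance table shows how much weight that assumption carries in each arm.

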Data and information contained in this document are considered to constitute trade secrets and confidential commercial information, and the legal protections provided to such trade secrets and confidential information are hereby claimed under the provisions of applicable law. No part of this document may be publicly disclosed without the written consent of Philip Morris Products S.A

Philip Morris Products SA.	Statistical Analysis Plan	Confidential
P1-EXC-01-EU	Final 2.0	Page 42 of 71
Related to PMI-RRP-WKI-112487		

will be excluded from this analysis. However, if the workload for all visits (V3, V4 and V43) were wrong but the same then the subject will be included in the analysis.

The comparisons of interest will follow Table 4 and Table 5 with estimates for within and between arms presented together with their 95% confidence intervals. A scatter plot of change in time to complete the test versus maximum work rate by arm will be plotted as well.

Other covariates may be added as deemed appropriate. Estimates of variability (e.g. "Covariance Parameter Estimates") from the statistical model will be reported (at least in the original statistical output listings) and may be used to power future similar studies.

A separate sensitivity analysis with all subjects including those with incorrectly calculated work load will be analyzed as well using the same analysis.

9.6.1.1.3 To assess the intensity of the exercise training in subjects participating in a training program switching to IQOS, continuing to smoke cigarettes and being smoking abstinent

The SAS procedure PROC MIXED will be used with the restricted maximum likelihood method for estimation of the intensity of exercise training in the various (cigarette, IQOS-1 and SA) arms over time. The change from baseline (defined as V5) in exercise intensity will be the endpoint with age, visit, sex, arm, visit*arm, baseline cigarette consumption at V1 and daily cigarette consumption as covariates. Endpoints to be analyzed as exercise intensity are

- Cumulative work produced during each training session (calories and calories/kg body weight)
- Average work rate during each training session (watt and watt/kg body weight)

Estimates of the endpoints at V14, V28, V42 (corresponding to the end of the 1st, 2nd and 3rd month of training) and their 95% confidence intervals will be presented as per the comparisons listed in Table 5 except for IQOS-2 and Dual-2 groups as they did not participate in any exercise training. Estimates of study arms and pairwise comparisons of study arms will be tabulated over all visits as well as separately for each visit.

An example of SAS code for the model to be used is provided below:

```
proc mixed data= _DATA_ method=reml order=data;
class SUBJECT VISIT ARM SEX CC_CONS_GRP;
model ENDPOINT = ARM SEX AGE CC_CONS_GRP DAILY_CC_USE VISIT VISIT*ARM
/ddfm = kr;
random SUBJECT / subject = SUBJECT;
repeated VISIT / type=ar(1) subject = SUBJECT;
lsmeans ARM / diff=control("CC") CL alpha=0.05 bylevel e;
lsmeans ARM / diff=control("IQOS-1") CL alpha=0.05 bylevel e;
lsmeans VISIT*ARM / diff=control("VISIT#X" "CC") CL alpha=0.05 bylevel e;
```

Confidentiality Statement

Philip Morris Products SA.	Statistical Analysis Plan	Confidential
P1-EXC-01-EU	Final 2.0	Page 43 of 71
Related to PMI-RRP-WKI-112487		SAP P1-EXC-01-EU

```
lsmeans VISIT*ARM / diff=control("VISIT#X" "IQOS-1") CL alpha=0.05 bylevel
e;
run;
```

Estimates of variability (e.g. "Covariance Parameter Estimates") from the statistical model will be reported (at least in the original statistical output listings) and may be used to power future similar studies.

The average work rate during each interval at each training session, average heart rate during each training session, time spent at various percentages of maximal work rate and time spent at various percentages of maximal heart rate will be summarized using only descriptive statistics. For the time spent at maximal work rate or heart rate the data will be summarized at V5, V14, V29 and V41 as subjects will be on training program 1 at these visits.

9.6.1.1.4 To evaluate changes in physiological parameters and perception of exertion and capacity in subjects switching to IQOS, continuing to smoke cigarettes and being smoking abstinent

The SAS procedure PROC MIXED will be used to estimate the differences in blood composition parameters (V43) and respiratory parameters (V4 and V43) from baseline (V3) with age, sex, Ccigarette consumption at V1 and daily cigarette consumption as covariates. For the respiratory parameters, visit and visit*arm will be covariates in addition to those specified previously. Also the baseline values of the parameters (V3) will be considered as a covariate and other clinically relevant covariates of interest may be added as deemed appropriate. The dependent variable will be the change from baseline.

Endpoints to be analyzed as physiological parameters (V43) are the following blood composition parameters

- Hemoglobin mass (g)
- Red blood cell volume (mL)
- Plasma volume (mL)
- Total blood volume (mL)

Endpoints to be analyzed as respiratory parameters (V4 and V43) are the following

- Ventilation (L/min)
- Respiratory rate
- VCO2 (L/min)
- Respiratory exchange ratio (RER) (VCO2 / VO₂).

Estimates of the endpoints and their 95% confidence intervals within each arm will be reported and also differences between arms (see Table 4 for analysis related to V4 and Table 5 for V43) will be estimated and reported together with their 95% confidence intervals. Boxplots of each

Confidentiality Statement

Philip Morris Products SA.	Statistical Analysis Plan	Confidential
P1-EXC-01-EU	Final 2.0	Page 44 of 71
Related to PMI-RRP-WKI-112487		SAP P1-EXC-01-EU

physiological and respiratory endpoint listed above will be plotted versus visit and by arm within each plot.

For capillary blood lactate levels during the VO₂max test, we will fit a 4 parameter sigmoidal model for each arm at V3 and V43 respectively. Letting y_{ij} be the lactate of subject i at time *j*, we have

$$y_{ij} = (\beta + \beta_i) + \frac{\alpha - (\beta + \beta_i)}{1 + \exp\left\{\delta(\ln\left(W_{ij}\right) - \ln\left(\eta + \eta_i\right))\right\}} + \varepsilon_{ij}$$

where W_{ij} is the work rate for subject *i* at time *j* α and β are the minimum and maximum lactate levels respectively. The parameter η_i represents the workrate that elicits a response midway between α and β_i , and δ is a shape parameter. Lastly, the error term is modelled as ε_{ij} . Note that β_i and η_i are modelled as random effects to allow for variations in the lactate curve between subjects. An example of the sas code is as shown below, starting parameters may be found using proc nlin without the random effects. The number of random effects may be adjusted depending on model fit.

```
proc nlmixed data= data ;
  parms b0=xx e0=xx a=xx d=xx s2=xx s2b1=xx s2b2=xx cb12=xx;
  beta = b0 + bi;
  eta = e0 + ei;
  pred = beta+(a-(beta))/(1+exp(d(ln(w)-ln(eta))));
  model vo2 ~ normal(pred,s2);
   random bi ei ~ normal([0,0],[s2b1,cb12,s2b2]) subject=subject;
run;
```

Using the fitted models, we will back-calculate the value of W^* (conditional on β_i and η_i) that elicits a response of y=4 mmol (Heck 1985) using the following formula for each arm and visit.

$$W^* = \hat{\eta} \left(\frac{\hat{\alpha} - 4}{4 - \hat{\beta}} \right)^{\frac{1}{\hat{\delta}}}$$

Note that $\hat{\alpha}$, $\hat{\beta}$, $\hat{\delta}$ and $\hat{\eta}$ are the respective estimates from the fitted model. Within each arm, we will present the change in workload at a lactate level of 4mmol from V3 to V43. The mean curve estimated from the model for Cigarette, IQOS-1, IQOS-2 and SA will be plotted versus workload for each arm and visit, in these plots a horizontal line at 4 mmol will be drawn as well. The same plot will be done for Cigarette, IQOS-1, IQOS-2, Dual-1 and Dual-2.

For the endpoints VO₂ and heart rate (V4 and V43), a linear mixed effects model will be used with the restricted maximum likelihood method for estimation of the parameter in the various (cigarette, IQOS-1 and SA) arms versus workload. Each endpoint will be fitted with workload, age, visit, sex, arm, visit*arm, baseline cigarette consumption at V1 and daily cigarette

Data and information contained in this document are considered to constitute trade secrets and confidential commercial information, and the legal protections provided to such trade secrets and confidential information are hereby claimed under the provisions of applicable law. No part of this document may be publicly disclosed without the written consent of Philip Morris Products S.A

Philip Morris Products SA.	Statistical Analysis Plan	Confidential
P1-EXC-01-EU	Final 2.0	Page 45 of 71
Related to PMI-RRP-WKI-112487		CAD DI EVC AL EU

consumption as covariates. Additional covariates may be added as appropriate based on the results of the step wise modelling in section 9.6.1.1.1.

The mean curve estimated from the model for the CIGARETTE, IQOS-1, IQOS-2 and SA arm will be plotted versus workload for each arm and visit. The curves will be plotted for CIGARETTE, IQOS-1, IQOS-2, Dual-1 and Dual-2 in one plot as well.

An example of SAS code for the model to be used is provided below:

```
proc mixed data= _DATA_ method=reml order=data;
class SUBJECT VISIT ARM SEX CC_CONS_GRP;
model ENDPOINT = WORKLOAD ARM SEX AGE CC_CONS_GRP DAILY_CC_USE VISIT
VISIT*ARM /ddfm = kr;
random SUBJECT / subject = SUBJECT;
run;
```

Estimates of variability (e.g. "Covariance Parameter Estimates") from the statistical model will be reported (at least in the original statistical output listings) and may be used to power future similar studies.

9.6.1.1.5 To monitor trends of daily physical activity levels during the study in subjects switching to IQOS, continuing to smoke cigarettes and being smoking abstinent

The SAS procedure PROC MIXED will be used with the restricted maximum likelihood method for evaluation of the aggregated data for step counts from the mobile health (mHealth) wearable in the study arms over time. For step count, the dependent variable will be the average step count by month, this is derived by averaging the daily step count from V4 to V14 (Month 1), V14 to V28 (Month 2) and V28 to V43 (Month 3) divided by the number of valid days during each defined period. For a definition of valid day for step count refer to section 9.1.6.

The variables Arm, Visit, Visit*Arm, Sex, age, and baseline cigarette consumption at V1, baseline step count (see section 9.1.3) will be considered as covariates, subject will be used as a random effect. The Kenward-Roger adjustment for degrees of freedom will be use.

Estimates of the monthly step count and their 95% confidence intervals within each arm will be reported and also between arms as per Table 5.

An example of SAS code for the model to be used is provided below:

```
proc mixed data= _DATA_ method=reml order=data;
class SUBJECT MONTH ARM SEX CC_CONS_GRP;
model ENDPOINT = ARM SEX AGE CC_CONS_GRP MONTH MONTH*ARM /ddfm = kr;
random SUBJECT / subject = SUBJECT;
lsmeans ARM / diff=control("CC") CL alpha=0.05;
lsmeans ARM / diff=control("IQOS-1") CL alpha=0.05;
```

Confidentiality Statement

Philip Morris Products SA.	Statistical Analysis Plan	Confidential
P1-EXC-01-EU	Final 2.0	Page 46 of 71
Related to PMI-RRP-WKI-112487		SAP_P1-EXC-01-EU
lsmeans MONTH*ARM / diff lsmeans MONTH*ARM / diff	ol("IQOS-2") CL alpha=0.05; =control("MONTH#X" "CC") CL =control("MONTH#X" "IQOS-1") =control("MONTH#X" "IQOS-2")	CL alpha=0.05;

The percentage of time active and percentage of time very active will be summarized on a monthly basis descriptively.

For each subject, average step counts will be plotted at baseline (V2-V3), Months 1 to 3. These will be presented as boxplots with step count on the y-axis and time on the x-axis for each product use group.

In addition, moving averages using a 7-day time window for daily step counts for all subjects will be plotted as well. If data is missing on one or more days, the average step count will be divided by the number of valid days available over the 7 day period. These will be plotted for all subjects versus day and color coded by product use arm. A separate plot will be created by averaging the daily moving average for each subject within a product use arm and plotted against time as well.

9.6.1.1.6 To describe changes in biological health markers in subjects switching to IQOS (with and without training), continuing to smoke cigarettes (with training) and being smoking abstinent (with training)

The SAS procedure PROC MIXED will be used with the restricted maximum likelihood method for evaluation of the biological health markers at V14, V28 and V43. The dependent variable will be the change from baseline of the biological health markers with age, sex, arm, visit, visit*arm, baseline cigarette consumption at V1 and daily cigarette consumption as covariates. Subject will be fitted as a random effect.

The baseline values of the parameters (V3) will be considered as covariate and other clinically relevant covariates of interest may be added as deemed appropriate. Estimates of the endpoints and their 95% confidence intervals within each arm will be reported and also between arms as per Table 5.

An example of SAS code for the model to be used is provided below:

```
proc mixed data= _DATA_ method=reml order=data;
class SUBJECT VISIT ARM SEX CC_CONS_GRP;
model CHANGE = BASELINE ARM SEX AGE CC_CONS_GRP DAILY_CC_USE VISIT
VISIT*ARM /ddfm = kr;
random SUBJECT / subject = SUBJECT;
lsmeans VISIT*ARM / diff=control("14" "CC") CL alpha=0.05 bylevel e;
lsmeans VISIT*ARM / diff=control("14" "IQOS-1") CL alpha=0.05 bylevel e;
lsmeans VISIT*ARM / diff=control("14" "IQOS-2") CL alpha=0.05 bylevel e;
```

Confidentiality Statement

Philip Morris Products SA.	Statistical Analysis Plan	Confidential
P1-EXC-01-EU	Final 2.0	Page 47 of 71
Related to PMI-RRP-WKI-112487		SAP P1-EXC-01-EU
	diff=control("28" "CC") CL alpha	-
lsmeans VISIT*ARM /	diff=control("28" "IQOS-1") CL a	lpha=0.05 bylevel e;
lsmeans VISIT*ARM /	diff=control("28" "IQOS-2") CL a	lpha=0.05 bylevel e;
lsmeans VISIT*ARM /	diff=control("43" "CC") CL alpha	=0.05 bylevel e;
lsmeans VISIT*ARM /	diff=control("43" "IQOS-1") CL al	lpha=0.05 bylevel e;
lsmeans VISIT*ARM /	diff=control("43" "IQOS-2") CL al	lpha=0.05 bylevel e;
run;		

9.6.1.1.7 To describe changes in weight, body fat and waist circumference in subjects switching to IQOS, continuing to smoke cigarettes and being smoking abstinent

The SAS procedure PROC MIXED as described above for biological health markers will be used to evaluate the change from baseline in body fat and waist circumference (V4 and V43) with age, sex, visit, product use, visit*product use and daily cigarette consumption as covariates. Subject will be fitted as a random effect. Also the baseline values of the parameters (V3) will be considered as covariate and other clinically relevant covariates of interest may be added as deemed appropriate. Estimates within and between groups similar to those shown in Table 4 and Table 5 will be provided.

For body weight, the model presented in section 9.6.1.1.3 will be used to assess the changes at V14, V28 and V43 with change from baseline (V3) as the endpoint and age, sex, visit, product use, visit*product use and daily cigarette consumption as covariates. Subject will be fitted as a random effect. Also the baseline values of the parameters (V3) will be considered as covariate and other clinically relevant covariates of interest may be added as deemed appropriate. Estimates within and between groups at V14, V28 and V43 will be calculated together with their respective 95% confidence intervals.

Box plots for the change from baseline in weight for the study arms by month will be presented. For body fat and waist circumference we will present the study arms side by side separately for each visit (V4 and V43).

9.6.1.1.8 To monitor levels of exposure to CO, nicotine, nitrosamines and acrylonitrile in subjects switching to IQOS, continuing to smoke cigarettes and being smoking abstinent

The corresponding endpoints, i.e. the exhaled CO and COHb% in blood, NEQ, NNAL and CEMA in urine (the latter three adjusted for creatinine) will be summarized descriptively, see Section 9.6.1.2.

Data and information contained in this document are considered to constitute trade secrets and confidential commercial information, and the legal protections provided to such trade secrets and confidential information are hereby claimed under the provisions of applicable law. No part of this document may be publicly disclosed without the written consent of Philip Morris Products S.A

Philip Morris Products SA.	Statistical Analysis Plan	Confidential
P1-EXC-01-EU	Final 2.0	Page 48 of 71
Related to PMI-RRP-WKI-112487		SAP P1-EXC-01-EU

